1) Asthma-related oral corticosteroid use; 2) Asthma-related ED visits 3) Asthma-related hospitalizations; 4) Asthma symptom control, as measured by the Asthma Control Test (ACT) for adults and childhood Asthma Control Test for children. In addition, patient demographics, co-morbidities, and parent and physician management factors (measured in aim 2 and 3) will be assessed.

We will use parent-report surveys of the following psychosocial outcome measures:

1) Days missed from school due to asthma; 2) Pediatric Asthma-Related Quality of Life (PACQLQ); and 3) Parental Asthma Management Self-Efficacy (PAMSE).

2) Enhance parental management through improved inhaler use.

We will use the Propeller Sensor Platform (referenced as Remote Health Management Platform) to allow parents to track their child's ICS and SABA inhaler use daily (please see the appendices for a list of inhalers that are compatible). The Platform also will have specific educational messaging to help parents and their children achieve adherence to their prescribed plan. This constant feedback and reinforcement may lead to improved asthma control therefore reducing frequency and severity of asthma exacerbations. We will also be assessing the factors associated with the feasibility and sustainability of the Propeller Sensor Platform by observing trends in utilization. Utilization and drop-off will be measured by monitoring use of the inhalers and periodic surveys of families.

3) Improve management by the healthcare team.

We will use the Remote Health Management Platform to integrate inhaler use data into a web portal that the physician's office can access. Through the development of this interface, the Propeller Sensor Platform will be able to provide inhaler use feedback to healthcare teams.

Types of feedback:

- Emergency Management: data on ICS and SABA use
- Long-term Management: data on ICS and SABA use

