| Parent-reported values (un-validated) | School days missed due to asthma | 5 times in total (baseline, 3 months, 6 months, 9 months, study completion) |
| Pediatric Caregiver Asthma-related Quality of Life Questionnaire (PACQLQ) | Parent form of how their child's asthma is affecting both their lives and the life of their child | 5 times in total (baseline, 3 months, 6 months, 9 months, study completion) |

Parental Management Outcomes

| Source | Outcome | Time Point |
|-----------------------------------|--|---|
| Parent report (Survey) | Feasibility and acceptability of Platform | 5 times in total (baseline, 3 months, 6 months, 9 months, study completion) |
| Remote Health Management Platform | Frequency of use of the application (synching) | Monthly data pull |

Physician and Clinical Team Outcomes

| Source | Outcome | Time Point |
|-----------------------------------|---|---|
| Remote Health Management Platform | ICS and SABA use | Monthly download |
| Web Portal/Epic | Asthma-related ED visits, hospitalizations, and oral corticosteroid prescriptions/courses | Monthly Epic data pull |
| Clinician Survey | Feasibility and acceptability of the Platform | 1 month into the study, 6 months and study completion |
| Physician Survey | Feasibility and acceptability of the Platform | 1 month and study completion |
| Remote Health Management Platform | Frequency of use of the web portal | Monthly data pull |

Data Analysis:

Primary Outcomes

- *ACT*: Parent-reported test on their child's asthma control
- *Asthma-related hospitalizations*: Data will be obtained from the EMR and parent report.
- *Asthma-related ED visits*: Data will be obtained from the EMR and parent report.
- *Asthma-related oral corticosteroid use*: Prescription/course data will be obtained from the EMR and parent report.

Secondary Outcomes

- *Inhaler Use*: Use data, including frequency of both SABA and ICS inhalers, will be obtained via the sensor throughout the study period.
- *PAMSE*: Parental Asthma Management Self-Efficacy; self-report survey that measures parental self-efficacy for the management and prevention of acute exacerbations of asthma.
- *PACQLQ*: Paediatric Asthma Caregiver's Quality of Life Questionnaire; will assess the impact of their child's asthma on their lives, the lives of their children with asthma, and the family as a whole.

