After the patient's enrollment visit, parents will be contacted via email or phone at 1, 3, 6, 9, and 12 months to complete a REDCap survey. Each quantitative survey item will be summarized using descriptive statistics such as frequencies and percentages along with any corresponding measures of spread. Qualitative data will be coded and analyzed by theme analysis.

The following questions will be asked:

Quantitative Questions:

1. How often do you check the sensor system?
 - More than once a daily
 - Daily
 - Once a week
 - More than once a week
 - Every other week
 - I don't check the Propeller Sensor (*If selected, participants will only answer question 1 and 5*)
2. How often in the past week did you receive useful asthma information through the sensor system?

- Once
 - Twice
 - Three or more times
 - I did not receive useful asthma information through the sensor system
3. How helpful is the sensor system in managing your child's asthma?
- Extremely helpful
 - Very helpful
 - Helpful
 - A little helpful
 - Not helpful
 - I have not checked the sensor system
4. What do you enjoy most about the sensor system?
- Easy to use
 - Ability to track inhaler use
 - Asthma Education cards
 - Other: *fill in the blank*
 - Nothing
5. Do you have any issues regarding the sensor system?
- *Comment Box*

AIM 3. Improve management by physician and clinical team.

On a biweekly basis, we will collect quantitative data from clinics on the number of time physicians' follow-up with patients and the follow-up outcome. The research team will know exactly how many alerts physicians are receiving, and how physicians are following-up with patients from the Propeller dashboard. The data from the Propeller dashboard will be summarized with descriptive statistics. Clinicians will also be contacted at 1, 3, 6, 9, and 12 months through REDCap surveys to determine if the data is helping them with management and aspects of the platform they like and dislike. Qualitative data will be coded and analyzed by theme analysis.

The following questions will be asked:

Quantitative Questions:

1. In the past week, how many times did you check the propeller dashboard?
 - Once time
 - Twice
 - 3 or more times
 - Zero
2. Are the Propeller Dashboard flags useful to you?
 - Yes
 - No
3. In the past week, how many times did you have to follow-up with patients due to alerts you received regarding the over use of Albuterol?
 - Once
 - Twice
 - 3 or more times
 - Zero

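### Item 1 of the Aim 2 caregiver survey has no answer for checking less often than fortnightly but more than never, which distorts the survey component of utilization and drop-off

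*Protocol*

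**What the plan says.** Protocol, Statistical Analysis, AIM 2, lists the caregiver survey given at 1, 3, 6, 9 and 12 months. Item 1 asks "How often do you check the sensor system". The answers, in the order printed, are more than daily, daily, weekly, more than weekly, "Every other week" and "I don't check the Propeller Sensor". Anyone choosing the last answer goes on to item 5 only, so items 2 to 4 are skipped.

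Protocol, Study Aims, Aim 2, gives the survey its purpose. The plan will assess factors associated with the "feasibility and sustainability of the Propeller Sensor Platform by observing trends in utilization", and it adds: "Utilization and drop-off will be measured by monitoring use of the inhalers and periodic surveys of families".

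On analysis, the Protocol summarizes each quantitative survey item descriptively. The SAP, AIM 2, does so at each time point and adds chi-squared tests of association with demographic predictors.

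The Protocol also has platform-based measures. The Parental Management Outcomes table lists "Frequency of use of the application (synching") as a monthly data pull. Under Secondary Outcomes, Inhaler Use, it states: "Use data, including frequency of both SABA and ICS inhalers, will be obtained via the sensor throughout the study period".

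**The concern.** A response scale for frequency should give every respondent one true answer, and this one does not. Checking less than fortnightly but more than never has no category. Item 4 offers a fill-in answer; item 1 does not. The gap lies at the step between declining use and stopping, which a drop-off question should be able to show.

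Three results are exposed. The first is the pair of percentages at the bottom of item 1, at each of the five surveys. The second is items 2 to 4 (useful information received, helpfulness, what is enjoyed most): an infrequent checker who picks the zero answer leaves those items, which can tilt them towards more engaged families. The third is the SAP's chi-squared tests. If demographic groups resolve the forced choice differently, an apparent association could come from the scale and not from behaviour.

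**Working it through.** The documents state no figure to reproduce, and no sample size, power or event rate enters. The check sets the option list against the uses made of it.

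**1. Is the scale exhaustive?** For each possible true frequency, the available answer is:

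| True frequency of checking | True answer available? |
|---|---|
| More than daily, daily, several times a week, weekly | Yes |
| Fortnightly | Yes |
| Monthly, or now and then | No |
| Never | Yes |

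The gap falls in a plausible range. The later surveys are three months apart, so a caregiver who checks once a month looks about three times between surveys (3 months × 1 per month) and still has no correct answer.

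**2. What happens to the item 1 percentages?** Among those who answer at a given survey, let *a*, *b* and *c* be the true shares who check fortnightly, less often than that, and never. Suppose a fraction *p* of the middle group rounds up and the rest round down.

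- Recorded as fortnightly: *a* + *pb*, too high by *pb*.
- Recorded as not checking: *c* + (1 − *p*)*b*, too high by (1 − *p*)*b*.
- Sum of the two: *a* + *b* + *c*, which is correct.

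The two errors add up to *b*, and each lies between 0 and *b*. The documents give neither *b* nor *p*. Assuming a value for *b* would only return that value as the maximum error, so no numerical size is offered. Blank answers would add item non-response on top. The combined share checking fortnightly or less, never included, is not affected by the gap among those who answer.

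**3. What of tapering is lost?** A move from daily to weekly to fortnightly fits the existing answers and shows across the five surveys. Only the step below fortnightly is lost.

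**4. Do other data fill the gap?** In part. Sensor data record inhaler actuations, and synching records data transfer. The Protocol's Technology section says the sensor transmits by Bluetooth to a paired smartphone or hub and uploads to the cloud. It is an inference from that description, not a statement in the plan, that synching need not mean anyone looked at the data. Item 1 is the only caregiver survey question on how often the system is checked.

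**5. What does the item feed?** It feeds the Aim 2 summaries and the SAP's chi-squared tests. It is not among the primary outcomes, it does not enter the Aim 1 models, and it plays no part in the Sample Size Determination.

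**The case against.** The strongest reply is that little depends on this item. Aim 2 names monitored inhaler use before the family surveys, and no section names item 1 as the drop-off measure. The Parental Management Outcomes table assigns feasibility and acceptability to the parent survey and gives frequency of app use to the platform. Research staff review uploaded sensor data daily (Study Design and Procedures, Intervention). Declining use can therefore be seen in objective data between surveys, whatever answers item 1 offers. The SAP attaches no stated hypothesis or decision to the chi-squared tests.

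Most of this stands, and it limits the point. A reader might infer that the drop-off measure as a whole is wrong. The documents do not support that, because monitored inhaler use and synching do not depend on item 1. A reader might also infer that families whose use is tapering are recorded as regular users. That does not follow either: fortnightly is the lowest non-zero category, the documents define no threshold for regular use, and tapering down to fortnightly stays visible.

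The reply does not remove the gap. Checking the system is a different behaviour from using an inhaler or transferring data, and the plan chose to ask about it. An item that is tabulated and tested at five time points should have a true answer for every respondent.

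**Conclusion.** The point holds as a minor design flaw in one feasibility item. Followed as written, item 1 misplaces or loses every caregiver who checks less than fortnightly but more than never. The percentages for the two lowest answers, and any association tested on them, are distorted by an unknown amount. That amount is zero if no such caregivers exist and is bounded by their share if they do. The skip rule carries part of the problem into items 2 to 4.

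The conclusion rests on the printed option list being the one used, and on some caregivers checking this rarely, which is plausible over a year of follow-up but not documented. The consequence stays within the survey component of utilization and drop-off.

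**What to change.** - Add an answer, *Less often than every other week*, immediately before the non-checking answer.
- List the answers in order of frequency; at present weekly is printed before more than weekly.
- Keep the skip to item 5 for true non-checkers only, so that caregivers who choose the new answer complete items 2 to 4.
- Report the already scheduled monthly synching data beside the self-report at each survey, noting that the two measure different things.

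The cost is one REDCap answer, a reordering and a short amendment. The real drawback is comparability. Answers given before the change cannot be separated afterwards from item 1 itself, so percentages before and after will not match at the low end. Report the two periods separately, or combine fortnightly, less often and never into one category for trends. Apart from blanks, that combined category has the same meaning before and after the change.

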4. In the past week, how many alerts did you receive due to patients overusing albuterol?
 - One
 - Two

- 3 or more
- 5. In the past week, how many times did you have to follow-up with patients regarding their underuse of their controller medication?
 - Once
 - Twice
 - 3 or more times
- 6. In the past week, how many alerts did receive due to patients underusing their controller medication?
 - One
 - Two
 - 3 or more
 - Zero
- 7. On a scale of 1-5 (1 being the least helpful, and 5 being the most helpful), how helpful do you feel calls to patients improve asthma management?
 - 1
 - 2
 - 3
 - 4
 - 5
- 8. On a scale of 1-5 (1 being the least useful, and 5 being the most useful) how much do you think the parents found your call useful?
 - 1
 - 2
 - 3
 - 4
 - 5

Qualitative Questions:

1. What do you find useful about the Propeller dashboard?
2. What changes do you think are needed to improve the Propeller dashboard?
3. How are you currently using the Propeller dashboard? Please describe.
4. Would you utilize the Propeller health management platform for your current practice in the future?

Sample Size Determination:

Assuming asthma exacerbation rate of 0.545 for the intervention arm, and asthma exacerbation rate of 0.75 for the standard treatment arm, resulting odds ratio (OR) equal to 0.3992674, and $\log(\text{OR}) = -0.9181239$. Assuming 20% patient drop-out rate, two-sided significance level $\alpha = 0.05$, a total of 250 patients (125 per arm) is needed in order to achieve a statistical power of 85%. The sample size calculation was computed using SAS procedure PROC SEQDESIGN.

Qualitative Analyses of Semi-Structured Interviews:

Data will be analyzed systematically using a constant comparative approach; and four analysts (i.e., coders), including [name] (qualitative methods expert), [name], and 2 research team members, will meet to discuss initial thoughts, insights, and observations for the development of initial coding categories (e.g., themes). Through a systematic analysis process, themes will be continually refined by collapsing redundant themes and removing irrelevant themes. Once no new categories have emerged, a

codebook will be developed for the remaining analysis. We will construct a saturation grid, to track themes as they emerge and determine when no new information is obtained

Study Staff:

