# Missing data and sensitivity analyses:

Missing data will be handled using Multiple Imputations. Sensitivity analyses will be conducted using SAS procedures PROC MI and PROC MIANALYZE. Other sensitivity analyses may be performed if appropriate.

AIM 2. Enhance parental management through improved inhaler use.

After the patient's enrollment visit, parents will be contacted via email or phone at 1, 3, 6, 9, and 12 months to complete a REDCap survey. Descriptive statistics (frequencies and percentages) of each quantitative question will be summarized at each time point and associations between outcomes and demographic predictors will be analyzed by Chi-squared test. Qualitative data will be coded and analyzed by theme analysis.

AIM 3. Improve management by physician and clinical team.

On a biweekly basis, we will collect quantitative data from clinics on the number of time physicians' follow-up with patients and the follow-up outcome. The research team will know exactly how many alerts physicians are receiving, and how physicians are following-up with patients from the Propeller dashboard. The data from the Propeller dashboard will be summarized and associations between outcomes and clinic predictors will be analyzed by Chi-squared test. Clinicians will also be contacted at 1, 3, 6, 9, and 12 months through REDCap surveys to determine if the data is helping them with management and aspects of the platform they like and dislike. Descriptive statistics (frequencies and percentages) from surveys will be summarized at each time point and associations between outcomes and clinic predictors will be analyzed by Chi-squared test.

Qualitative data will be coded and analyzed by theme analysis.

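### Clinician survey items 4 and 5 cannot record zero, so their frequencies either overstate activity or confuse a true zero with non-response

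*Protocol*

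**What the plan says.** The Protocol, under Statistical Analysis, Aim 3, prints the clinician survey items with their answer options. Five of them ask for a count over the past week:

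- Item 1, dashboard checks: "In the past week, how many times did you check the propeller dashboard". Zero is offered.
- Item 3, follow-ups "due to alerts you received regarding the over use of Albuterol". Zero is offered.
- Item 4, albuterol-overuse alerts: "In the past week, how many alerts did you receive due to patients overusing albuterol". One, two, or three or more; no zero.
- Item 5, controller-underuse follow-ups: "In the past week, how many times did you have to follow-up with patients regarding their underuse of their controller medication". Once, twice, or three or more; no zero.
- Item 6, controller-underuse alerts: "In the past week, how many alerts did receive due to patients underusing their controller medication". Zero is offered.

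No skip rule or not-applicable option is printed for these items. For the analysis, the SAP (Aim 3) states: "Descriptive statistics (frequencies and percentages) from surveys will be summarized at each time point". It adds chi-squared tests of association with clinic predictors.

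The same part of the Protocol describes two other sources for these quantities. On alerts: "The research team will know exactly how many alerts physicians are receiving", from the Propeller dashboard. On follow-ups: "On a biweekly basis, we will collect quantitative data from clinics on the number of time physicians' follow-up with patients".

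**The concern.** Three of the five past-week count items let a clinician answer zero and two do not. Nothing in the text explains the difference, so it reads as an oversight. A clinician who had no albuterol-overuse alerts, or made no controller-underuse follow-ups, has no truthful option to tick.

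The gap also produces contradictory answers within one form. A clinician can report zero controller-underuse alerts on item 6, but any answer to item 5 claims at least one follow-up for underuse. A clinician who answers zero on item 3 and ticks anything on item 4 appears to have received an overuse alert and not acted on it.

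At stake is whether the tabulated percentages for items 4 and 5, and the chi-squared tests on them, can be taken at face value.

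**Working it through.** The plan states no figure for these items, so there is none to reproduce. The check compares the printed answer sets and then works out what the missing option does to the planned summaries.

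**Step 1: Is the omission real?** Where zero is offered (items 1, 3 and 6), it is the last option. The option list of item 4 is interrupted in the text between its second and third options, not at the end. The list of item 5 is not interrupted. A zero option lost in converting the document is therefore unlikely for either item.

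**Step 2: Direction.** Let q be the true share of clinicians with a zero count in the week. The documents do not give q, so a range is shown. For illustration, assume that non-zero counts split equally over the three options and that three or more is scored as 3. The mean among non-zero clinicians is then (1 + 2 + 3)/3 = 2.

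- True share with at least one: 1 − q. True mean: 2(1 − q).
- If zero-count clinicians skip: every answer is at least one, the mean among answers is 2.0, and item response falls to 1 − q.
- If they tick the lowest option: every answer is at least one, and the mean is q + 2(1 − q).

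| q (assumed) | True share with at least one | Share among answers, either route | True mean | Mean if zeros skip | Mean if lowest ticked |
|---|---|---|---|---|---|
| 0.1 | 90% | 100% | 1.8 | 2.0 | 1.9 |
| 0.3 | 70% | 100% | 1.4 | 2.0 | 1.7 |
| 0.5 | 50% | 100% | 1.0 | 2.0 | 1.5 |
| 0.7 | 30% | 100% | 0.6 | 2.0 | 1.3 |
| 0.9 | 10% | 100% | 0.2 | 2.0 | 1.1 |

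The SAP plans percentages, not means; the mean is used here only as a compact summary. The 100% column follows from the answer set and carries no information about activity.

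**Step 3: The denominator.** Take q = 0.5. Each non-zero option has a true share of (1 − 0.5)/3 = 16.7%.

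- Zeros skip, percentages of responders: each option shows 33.3%, which is overstated.
- Zeros skip, percentages of all clinicians surveyed: each option shows 16.7%, which is correct. The remaining 50% is blank, and true zeros cannot be separated from non-response.
- Zeros tick the lowest option: that option shows 0.5 + 0.167 = 66.7%, which is overstated.

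The SAP does not state the denominator. It names multiple imputation in general terms, with no rule for survey items. Imputing blanks from the three observed categories would bring the overstatement back, because no zero category exists to impute.

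**Step 4: The chi-squared tests.** Suppose two clinics differ only in q, at 0.1 and 0.9. If zeros skip, both show one third in each option among responders, so the test is blind to the difference. If zeros tick the lowest option, its share is 0.1 + 0.9/3 = 40% in one clinic and 0.9 + 0.1/3 = 93.3% in the other. The difference then shows, but as one against more than one instead of none against some.

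**The case against.** The strongest reply is that little depends on these items. Alerts are logged by the dashboard and follow-ups are collected from clinics every two weeks, so both quantities have a source that the answer options cannot distort. The Protocol's outcome table for physicians and the clinical team lists the surveys under feasibility and acceptability of the platform, not as a measure of activity. All of this stands, and it limits the point to two descriptive items. It does not make the tabulated percentages for those items correct. If survey and dashboard disagreed, no one could tell whether the cause was clinicians' perception or the form.

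A reader might infer that the Aim 3 activity results as a whole are biased upward. The documents do not support that: items 1, 3 and 6 and both independent sources are untouched. For items 4 and 5 themselves, overstatement depends on how zero-count clinicians respond and on the denominator, as step 3 shows.

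A reader might also put a size on it, for example that the share with at least one follow-up would be reported as 100% when the truth is 40% to 70%. That range is only 1 minus an assumed zero share of 60% to 30%. It also needs percentages among those who answer, and a summary of at least one, which the SAP does not name. Nothing in the documents shows how common zero is.

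Neither document plans to compare item 3 with item 5 or item 4 with item 6, so the contradictory pairs are a data-quality problem and not a failed analysis.

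Finally, the fielded form cannot be seen. The physician questionnaires are listed among the appendices, but their content is not in the text available. The Protocol's clinical management outcome also describes a four-question survey of the healthcare team, whereas eight quantitative items are printed under Aim 3. The point therefore applies to the items as printed.

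**Conclusion.** The point holds for the two items as printed, and it is minor. Items 4 and 5 cannot record zero, although the parallel items 1, 3 and 6 can. Their frequencies and chi-squared tests will either overstate activity or leave true zeros mixed with non-response. Which of these occurs depends on clinicians' behaviour and on a denominator that the SAP does not state.

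The size cannot be determined from the documents; the tabulated values rest on assumed zero shares and an assumed equal split of the non-zero counts. Dashboard alert counts, biweekly follow-up counts, the primary outcomes and the comparison between arms are not affected.

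**What to change.** Add a zero option to items 4 and 5, matching items 1, 3 and 6. In the SAP, state the denominator for the clinician survey percentages and how blank items are handled. The cost is one answer option in each of two REDCap items and a sentence in the SAP.

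If the survey has already been fielded, first check the REDCap form. If zero was missing there too, take alert counts from the dashboard and follow-up counts from the biweekly clinic data. Do not report the share with at least one from items 4 and 5, and do not impute their blanks from the three offered categories. This needs no new data collection.

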The site investigator will assign the randomized treatment to a patient in the sequential order, based on the stratum the patient belongs to.

7. Intervention

- a. After enrollment, participants in the Remote Health Management Sensor group will have the full Remote Health Management Sensor Platform (i.e. mobile application, physician access to inhaler use data, etc.). Research staff will review uploaded sensor data on a daily basis. If participants are enrolled into the control group, they will only receive Standard Asthma Education. The Standard Asthma Education follow the NAEPP (National Asthma Education and Prevention Program) guidelines for asthma management. This will include the following list of topics: 1. What is Asthma (Explanation of symptoms); 2. Asthma triggers (what those are and how to avoid them); 3. Using medications (how to use prescribed asthma medications, the difference between controller medications and rescue inhalers, how to appropriately use a spacer, how to appropriately use a mask); and 4. Managing asthma control (purpose of asthma control test and how to complete it, purpose of an asthma action plan and how to read and complete it, how to appropriately use a peak flow meter).

- b. All participants will receive allergen testing, done by their physicians to ascertain their environmental triggers. This will be incorporated into the Remote Health Management software for the intervention group.
- c. If uploaded data reveals elevated SABA use, healthcare team staff will be expected to contact caregivers if needed to ascertain the context of the elevated use and schedule appointments as needed. Information regarding this contact will be documented in the patient's EMR and available to researchers.
- d. The Remote Health Management Platform will send education, based on management plan and identified asthma triggers, to participant in the intervention group.

8. 1 month from start of enrollment

- a. Control Arm- Caregivers will take the ACT, PAMSE, iTRACC survey, and PACQLQ. Caregivers will also be asked about acute exacerbations, ED visits, and hospitalizations as visits to out-of-network healthcare facilities may not be visible in the EMR. This information will be collected via email or phone for both groups utilizing a REDCap survey link for each participant.

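### Clinician survey item 8 rates a call but gives no answer for clinicians who made none, so its tabulation may mix ratings with and without call experience

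*Protocol*

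**What the plan says.** Item 8 of the clinician questions (Protocol, Statistical Analysis, Aim 3) asks for a score from 1 to 5 on "how much do you think the parents found your call useful". The five scores are the only answers printed. Item 7 uses the same scale but asks a broader question: "how helpful do you feel calls to patients improve asthma management".

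Two other items in that list count follow-ups in the past week. Item 3 asks "how many times did you have to follow-up with patients due to alerts you received regarding the over use of Albuterol" and includes Zero among its answers. Item 5 asks "how many times did you have to follow-up with patients regarding their underuse of their controller medication" and prints no Zero.

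Protocol section 7 (Intervention), point c, describes what follows when the uploaded data show high SABA use: "healthcare team staff will be expected to contact caregivers if needed".

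The caregiver survey under Aim 2 handles lack of experience explicitly. Caregivers who answer item 1 by saying that they do not check the sensor are routed past the rating items: "If selected, participants will only answer question 1 and 5". Item 3 there, "How helpful is the sensor system in managing your child's asthma", also has an answer for people who have not looked at the system.

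For the clinician surveys, the SAP (Aim 3) plans frequencies and percentages at each time point, and states that "associations between outcomes and clinic predictors will be analyzed by Chi-squared test". It does not limit any item to respondents who made calls.

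**The concern.** Item 8 presupposes that the respondent placed a call. A clinician who placed none can only guess a score or leave the item blank. If some guess, the reported distribution combines judgements of real contacts with scores that refer to nothing. A clinic with few alerts, or one where other staff do the telephoning, could then look different from a busy clinic because more of its respondents had no call to judge.

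Outreach prompted by the portal is a central part of Aim 3, and the Protocol means to assess wider implementation. How useful clinicians think their calls were is a reasonable thing to report, and readers will assume that the scores come from people who made calls.

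**Working it through.** The plan gives no figure on this point, so there is none to reproduce. The check sets the items side by side and then follows the effect through the statistic that the SAP plans.

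**1. Can a respondent have made no call?** Yes, on the plan's own terms. Contact depends on need and falls to healthcare team staff, so the surveyed clinician need not be the person who telephones. Item 3 offers Zero as an answer.

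**2. What can that respondent record on item 8?** A score from 1 to 5, or nothing. No other answer and no branching are printed.

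**3. Can callers be identified afterwards?** Not reliably.
- Items 3 and 5 cover one week, while item 8 has no recall period. Zero on item 3 does not show that no call was ever made.
- Item 3 covers only albuterol overuse. Item 5 covers controller underuse and has no Zero, so the two together do not identify a respondent without follow-ups even for that week.
- The biweekly follow-up data are collected from clinics. No link from those data to the individual survey respondent is described.

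**4. What happens to the planned statistic?** The SAP plans percentages, so take the percentage choosing score k. Among those who score item 8, define:
- f: the share who made no call
- p_k: the proportion of callers choosing k
- q_k: the proportion of non-callers choosing k

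The tabulated proportion is T_k = (1 − f) p_k + f q_k.

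Its departure from the callers' proportion is T_k − p_k = f (q_k − p_k).

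This is zero if no non-caller scores the item (f = 0) or if the two groups answer alike (q_k = p_k). Because q_k − p_k lies between −1 and 1, the departure cannot exceed f in either direction.

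For two clinics A and B with the same p_k and the same q_k, the difference is T_k(A) − T_k(B) = (f_A − f_B)(q_k − p_k). Callers in both clinics gave the same ratings, yet the clinics differ whenever their non-caller shares differ and non-callers answer differently. The chi-squared test would treat that as a clinic association.

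The documents give no value for f, p_k or q_k. The formulas show the direction of the problem and an upper bound, but not its size.

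**5. Is the omission consistent with the rest of the plan?** No. The caregiver survey uses both a skip rule and a no-experience answer for the same kind of question. Item 8 has neither.

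**The case against.** Several stronger readings are tempting, and the documents do not support them.

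- A reader might infer that every clinician is made to rate the calls. Nothing says that the items are mandatory. If non-callers leave item 8 blank, the mixing does not arise, although a blank then cannot be told apart from ordinary non-response.
- A reader might infer that the ratings of calls are not based on experience. Clinicians who called do answer from experience. The supportable statement is that the two kinds of answer may be mixed.
- A reader might extend the point to item 7. That item asks for an opinion on calls in general, which someone who made none can validly give. Removing those respondents would discard legitimate answers.
- A reader might infer that the trial uses item 8 as the parents' own view. The item openly asks what the clinician thinks, and no section treats it as parent-reported.
- A reader might want the bias expressed as a shift in the mean score. The SAP plans no mean for this item, and any such figure would rest wholly on invented inputs.

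It is also fair to say that follow-up is captured elsewhere: in the biweekly counts and outcomes, on the dashboard, in the medical record after elevated SABA use, and in the secondary outcome on clinical management, which is measured by completed tasks. Interviews after the trial may bring out families' views, but only from interested intervention-arm caregivers and without calls named as a topic. Finally, the full questionnaires are listed as appendices but are not reproduced in the text available, so all statements about missing options or items apply to the printed lists.

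These objections narrow the point to item 8. They do not supply its missing answer option or limit its analysis to callers.

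**Conclusion.** The point holds for item 8 only, as an inexpensive improvement to a descriptive measure. Analysed as written, its distribution may combine ratings with and without call experience, and clinics may differ through the share of non-callers. The other survey items cannot reliably separate the two groups. The conclusion assumes that the printed list is the form as fielded and that at least some non-callers give a score.

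The size is unknown. It runs from nothing up to a ceiling equal to the share of scorers who made no call, and the documents do not give that share. The primary outcomes, the sample size and the randomised comparison are unaffected.

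A related gap is that none of the five listed caregiver items asks about contact from the clinic. That is a reason to consider adding a question. It is not evidence that the plan misuses item 8.

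**What to change.** 1. Add an answer to item 8 for clinicians who have made no calls since the last survey (at the first survey, since the study began).
2. In the SAP, state that item 8 is tabulated and tested among callers only, with the number of non-callers shown beside it at each time point.
3. Report item 8 as usefulness as perceived by the clinician.
4. Leave item 7 open to all respondents as a general opinion, shown by caller status if wished.
5. Optionally, add one branched question to the intervention-arm caregiver survey: whether the clinic has been in contact about inhaler use since the last survey and, if so, how useful that was on a 1 to 5 scale.

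The cost is one response option in a REDCap form that is already sent and a sentence or two in the SAP. The denominator for item 8 becomes smaller, and the optional step adds one question for caregivers.
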